## 4.0 Number of Participants

### 4.1 Total number of participants to be accrued:

We expect to enroll approximately 450 participants.

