### 4.2 Number of participants needed to complete the research procedures:

To achieve adequate statistical power, 358 participants with negative at-school BinaxNOW tests need to complete the research procedures, including the at-home BinaxNOW test.

An additional 50 participants with positive at-school BinaxNOW tests need to provide lollipop swabs.

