### 20.3 Participant Population for Analysis:

For Aim 1, we will include all participants who complete the at-home BinaxNOW test within 72 hours (N=358) and have nasal PCR results. For Aim2, we will include all participants who have both nasal and lollipop PCR results.

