### 20.4 Statistical Methods:

**Aim 1.** Sensitivity, specificity, positive predictive value (PPV) and NPV of the proposed BinaxNOW testing procedure for symptomatic subjects will be calculated and reported along with the corresponding two-sided 95% confidence interval. Formal non-inferiority testing of the BinaxNOW testing procedure with PCR will be conducted with respect to sensitivity and specificity with a non-inferiority margin of  $\delta=5\%$  and a sensitivity/specificity of PCR of 99%.

**Aim 2.** Results obtained from nasal and lollipop swab-based PCR testing will be summarized in tabular format. Concordance between the PCR test results will be evaluated by calculating the Kappa statistic which will be reported along with corresponding two-sided 95% confidence interval. The nonparametric bootstrap technique will be used to construct the confidence interval. A kappa statistic of  $>0.95$  will be considered as sufficient to define lollipop swab test non-inferior to the gold-standard PCR testing of nasal swabs. Furthermore, standard diagnostic test outcomes, i.e., sensitivity, specificity, NPV and PPV will be calculated (using the nasal swab-based

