## PROTOCOL TITLE: SAFE AND HEALTHY SCHOOLS

testing as gold standard), and reported along with the corresponding two-sided 95% confidence intervals. Formal non-inferiority testing of the lollipop swab test with PCR will be conducted with respect to sensitivity and specificity with a non-inferiority margin of  $\delta=5\%$  and a sensitivity/specificity of PCR of 99%. Statistical analyses will be conducted using SAS software (SAS Institute, Cary NC), version 9.4 or greater.

20.6 Handling of Missing Data: The primary analysis for evaluating the diagnostic utility of the BinaxNOW testing procedure will be based on the complete case principle. Since the analyses of this study won't involve any formal multivariate or longitudinal statistical modeling, no imputation-based analyses will be conducted.

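### The planned bootstrap interval for kappa has no provision for sparse discordance: it shrinks to [1, 1] with no discordant pairs and sits somewhat too high with a few

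*Combined protocol and SAP*

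**What the plan says.** For Aim 2, Section 20.4 measures agreement between the two PCR results by kappa and attaches a two-sided 95% interval. The method for that interval is then named: "The nonparametric bootstrap technique will be used to construct the confidence interval". The section does not give the variant (percentile, BCa, bootstrap-t), the number of resamples, the resampling unit, or a fallback for few or no discordant pairs.

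The success criterion is a kappa statistic above 0.95, which "will be considered as sufficient to define lollipop swab test non-inferior to the gold-standard PCR testing of nasal swabs". It is written on the statistic, not on a confidence limit. The section also plans sensitivity, specificity, PPV and NPV with two-sided 95% intervals, and a formal test of the lollipop on sensitivity and specificity against a 5% margin.

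On the analysis set, Section 20.3 says: "For Aim2, we will include all participants who have both nasal and lollipop PCR results". Section 4.1 gives the upper size, "We expect to enroll approximately 450 participants", and Section 4.2 asks for 358 completers with a negative at-school antigen test, then adds: "An additional 50 participants with positive at-school BinaxNOW tests need to provide lollipop swabs". No sample size, precision target or expected discordance is given for kappa.

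**The concern.** A nonparametric bootstrap can only reuse the pairs that were observed. If no pair disagrees, no resample can contain a disagreement. If one or two disagree, the resamples understate how many more disagreements the data are compatible with. Kappa above 0.95 at this sample size is by construction a table with very few discordant pairs, so a successful lollipop result falls where the named method is weakest. The pilot in Section 2.2 (25 of 25 symptomatic and 5 of 5 asymptomatic infected patients detected) makes a near-perfect table plausible. The risk is a published interval for kappa with zero width, or with a lower limit that is too high, read as settled agreement.

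**Working it through.** **The plan's own figure.** The only computed size is N=358 for Aim 1 (Section 20.2). An exact one-sided binomial test of 0.91 against 0.95 reproduces it: rejecting at 335 or more of 358 has size 0.0487 and power 0.909. There is no corresponding figure for kappa to reproduce.

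**Inputs.**
- Pairs: 358 + 50 = 408, up to about 450 (Sections 4.1, 4.2, 20.3).
- Nasal-PCR positives: not stated. Assumption: all 50 antigen-positive participants are PCR-positive, plus 1% to 9% of the antigen-negatives (9% is the complement of the 91% single-test NPV in 20.2). This gives 50 + 0.01 × 358 ≈ 54 up to 50 + 0.09 × 400 = 86, or 13% to 20% overall.
- Discordant pairs split evenly between the two directions (assumption).

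**Step 1: discordant pairs that success allows.** With positive share π, chance agreement is pe = π² + (1−π)², and for d discordant pairs among n, kappa ≈ 1 − (d/n)/(1−pe).
- 54 of 408: 1−pe = 0.2297. d=4 gives 1 − 0.00980/0.2297 = 0.957; d=5 gives 0.947. Maximum 4.
- 86 of 450: 1−pe = 0.3092. d=6 gives 1 − 0.01333/0.3092 = 0.957; d=7 gives just under 0.950. Maximum 6 (7 only if every discordant pair is a lollipop positive with a negative nasal result).

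**Step 2: the interval for a given table.** For d=0 every resample has kappa 1, so no variant can place a limit below 1. As a comparator, take the upper 95% Clopper-Pearson limit u for the discordance rate and convert it: lower limit = 1 − u/(1−pe). For d=0 and n=408, u = 1 − 0.025^(1/408) = 0.0090, so the limit is 1 − 0.0090/0.2297 = 0.961. For d=1, u = 0.0136 and the limit is 0.941.

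| Positives / pairs | Discordant | Percentile bootstrap lower limit | Clopper-Pearson-based lower limit |
|---|---|---|---|
| 54 / 408 | 0 | 1.000 | 0.961 |
| 54 / 408 | 1 | 0.964 | 0.941 |
| 54 / 408 | 2 | 0.944 | 0.923 |
| 54 / 408 | 4 | 0.910 | 0.892 |
| 86 / 450 | 0 | 1.000 | 0.974 |
| 86 / 450 | 1 | 0.976 | 0.960 |
| 86 / 450 | 2 | 0.963 | 0.948 |
| 86 / 450 | 6 | 0.919 | 0.907 |

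Once d is at least 1, the gap is about 0.01 to 0.02.

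**Step 3: how often [1, 1] occurs.** At true kappa κ the discordance rate is q = (1−κ) × 2π(1−π), and P(d=0) = (1−q)^n. At κ = 0.99: for n=408 and π=0.13, q = 0.00226 and P = 0.40; for n=450 and π=0.19, q = 0.00308 and P = 0.25. At 0.98 the same two cases give 0.16 and 0.06, at 0.97 about 0.06 and 0.015, and at 0.95 under 0.01.

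**Step 4: coverage by simulation** (4,000 trials per scenario, 4,000 resamples each; 408 pairs at 13% and 20% positive, 450 at 19%).

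| True kappa | Percentile coverage | BCa coverage |
|---|---|---|
| 0.95 | 92.5–93.4% | 96–97% |
| 0.97 | 90–93% | 92–97% |
| 0.98 | 84–93% | 82–92% |
| 0.99 | 59–75% | 58–74% |

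A separate run at kappa 0.985 with 408 pairs gave 76%. From 0.98 upward the shortfall is essentially P(d=0): at 0.99, 1 − 0.40 = 0.60 and 1 − 0.25 = 0.75. Misses are almost all intervals lying too high; even at 0.95 they are 5 to 6% above against about 1% below. A Dirichlet(0.5) interval on the four cells covers about 94 to 96% in the same settings.

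**The case against.** A reader might infer that the interval is far too optimistic across the whole range the plan calls success. The figures do not support that. At a true kappa of 0.95 to 0.97 the percentile interval loses only a few points of coverage, and BCa, which the wording permits, is close to nominal. If the lollipop performs at 99% sensitivity and specificity (an assumption, borrowing the figure that 20.4 gives for PCR), true kappa is about 0.957 to 0.968, percentile coverage is 91 to 94%, and [1, 1] appears in only 1 to 2% of trials. Severe failure needs near-perfect agreement, which the pilot is compatible with but does not establish.

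A reader might also infer that this interval is the only uncertainty shown for the lollipop, or that it could alter the declared outcome. Neither holds. Section 20.4 plans intervals for sensitivity, specificity, PPV and NPV as well. With no misses among 54 to 86 positives, an exact sensitivity interval would start at 0.025^(1/54) = 93.4% to 0.025^(1/86) = 95.8%, so uncertainty would be visible there (the plan does not name the method for those intervals). The success rule reads the point estimate. Even at zero discordance a valid lower limit stays above 0.95.

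One further objection is fair: a Dirichlet interval assumes independent pairs, whereas Section 7.5 allows repeat participation and Section 8.1 several children per family. A bootstrap of individual pairs makes the same assumption.

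These objections limit the scope of the point. They do not answer the degenerate interval or the optimistic lower limit, and the plan provides for neither.

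**Conclusion.** The point holds as a flaw in the reported precision of kappa. Followed as written, Section 20.4 would print [1, 1] for a table with no discordant pairs, and with the percentile variant a lower limit about 0.01 to 0.02 too high for a table with a few. Loss of coverage is moderate at a true kappa of 0.95 to 0.97 (about 90 to 94%), larger near 0.98 to 0.985 (about 76 to 93%) and severe at 0.99 (about 60 to 75%).

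It does not change the declared Aim 2 result. It could mislead someone who compares the printed lower limit with 0.95: with 54 of 408 positive and one discordant pair, 0.964 is above that value and 0.941 is below it.

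The sizes rest on the assumed positivity, an even split of discordant pairs and independent pairs. The [1, 1] result at zero discordance rests on none of these.

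**What to change.** In Section 20.4, replace the bootstrap sentence with an interval for kappa that is valid at the boundary: for example a Dirichlet(0.5), profile-likelihood or score/exact-type interval based on the cell probabilities of the 2×2 table. If the bootstrap is kept, name the variant and the resampling unit, and prespecify such an interval for use when discordant pairs are zero or fewer than a stated number. Naming BCa alone is not enough, because it fails in the same way from about 0.98 upward.

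The cost is one sentence and a few lines of code, with no extra participants or data, and a slightly wider interval. Whether the success rule should move from the point estimate to the lower limit is a separate question with its own cost in power, and this change does not depend on it.

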## 18.0 Sharing of Results

## PROTOCOL TITLE: SAFE AND HEALTHY SCHOOLS

18.1 Since the lollipop PCR test is investigational, the results will not be shared with participants or others. If the at-home BinaxNOW test is positive, the study team member will encourage the participants to follow up with their primary care provider. The school will receive the results of the nasal PCR from Exact Sciences or ACL, and that result will govern whether the child is permitted to return to school when symptoms resolve (if PCR is negative) or is required to stay at home for 10 days (if PCR is positive). As the resulting lab, Exact Sciences and ACL are responsible for reporting the nasal PCR results to Dane County Department of Health Services. Since the lollipop swab is investigational, results do not need to be reported to health officials.

For overall care management and recommendations, the study team is deferring to the school, which conducts and receives results of the nasal swab PCR result. Since this is the clinical test, the investigators would not recommend changing care management based on the exploratory test results in this study (lollipop swab and BinaxNOW). Any time an at-home BinaxNOW test is positive, the study team will encourage participants to follow up with the school and/or their PCP for recommendations. In short, the overall care plan will be based on the nasal swab PCR and managed by the school.

18.2 The results of this study will be published and accessible to the public.

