## PROTOCOL TITLE: SAFE AND HEALTHY SCHOOLS

subjects after a single test) versus the alternative hypothesis that the NPV is greater than 91%.

Aim 2: The lollipop swab test will be non-inferior to the gold-standard PCR testing of nasal swabs.

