### 20.2 Sample Size Justification:

For Aim 1, it is anticipated that the majority of initial BinaxNOW tests will be negative. It is hypothesized that the proposed two-day serial testing procedure using BinaxNOW tests in participants with an initial negative test will identify true negatives in >95% of participants. The primary diagnostic outcome measure will be the negative predictive value (NPV). The NPV of BinaxNow is ~91% in symptomatic subjects. For the proposed study, the NPV after the second test (24 hours after the first negative results), is assumed to be substantially higher than 91% since the first test was already negative. In order to detect a true NPV after the second test of at least 95% with 90% power at the one-sided 0.05 significance level, a sample size of N=358 participants with an initial negative test is required. To reach a sample size of N=358 participants with an initial negative test, BinaxNOW kits will be administrated to 400 participants. We intend to continue enrolling until we reach the target sample size of N=358 completing the at-home BinaxNOW test.

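### Aim 2 has two unranked non-inferiority rules; read literally, kappa above 0.95 can declare the lollipop swab non-inferior when the formal test fails

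*Combined protocol and SAP*

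**What the plan says.** Section 20.1 states the Aim 2 hypothesis as "The lollipop swab test will be non-inferior to the gold-standard PCR testing of nasal swabs". It names no measure and no margin.

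Section 20.4 then gives two routes to that conclusion:

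- **Kappa.** Agreement is assessed by "calculating the Kappa statistic which will be reported along with corresponding two-sided 95% confidence interval", with the interval obtained by bootstrap. A kappa statistic above 0.95 "will be considered as sufficient to define lollipop swab test non-inferior to the gold-standard PCR testing of nasal swabs". The interval plays no part in this rule.
- **Formal test.** Sensitivity, specificity and predictive values against nasal PCR are to be "reported along with the corresponding two-sided 95% confidence intervals". Then: "Formal non-inferiority testing of the lollipop swab test with PCR will be conducted with respect to sensitivity and specificity", with a 5% margin and PCR sensitivity and specificity set at 99%.

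Nothing says which rule governs, whether both are needed, or what follows if they disagree. The only significance level in the plan is in section 20.2, for the Aim 1 negative predictive value: "with 90% power at the one-sided 0.05 significance level, a sample size of N=358 participants with an initial negative test is required". The analysis set is in section 20.3: "For Aim2, we will include all participants who have both nasal and lollipop PCR results".

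**The concern.** Lollipop performance is one of the four primary objectives in section 1.0, and section 18.2 says the results will be published. As worded, the kappa rule is enough by itself, so the study could report non-inferiority while missing its own sensitivity margin.

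The cause is structural. Kappa pools missed cases and false positives into one figure. When most participants are PCR-negative and false positives are rare, kappa can stay high although an appreciable share of the positives is missed.

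The missing alpha adds a second freedom. With few positives, the choice between one-sided 0.05 and 0.025 can decide the formal result, and the plan leaves that choice open until the data are seen.

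**Working it through.** **The plan's own figures.** Aim 2 has no sample size, power or alpha to reproduce. The one computed figure, N=358, belongs to Aim 1. It reproduces by exact binomial (91% against 95%, one-sided 0.05: alpha 0.0487, power 0.909) and has no bearing here. The Aim 2 bound follows from section 20.4: 99% − 5% = 94%, read as a fixed bound.

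**Assumptions not in the documents.**
- N = 450, the enrolment target.
- 50 to 86 nasal-PCR positives: the 50 antigen-positives, plus 0–9% of the 400 initial negatives (9% from the quoted predictive value of about 91%; 0.09 × 400 = 36).
- Exact (Clopper–Pearson) lower bounds at one-sided 0.05.
- Lollipop specificity against nasal PCR is not projected in the plan, so it is varied.

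**Step 1: can the rules conflict?** Kappa = (Po − Pe)/(1 − Pe). Take 50 positives, 4 missed, no false positives, 400 true negatives:
- Po = 446/450 = 0.9911
- Pe = (46×50 + 404×400)/450² = 163,900/202,500 = 0.8094
- kappa = (0.9911 − 0.8094)/(1 − 0.8094) = 0.953
- sensitivity = 46/50 = 92.0%

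Kappa passes. Observed sensitivity is already below 94%, so no lower bound can clear 94%, whatever the test.

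| Missed / positives | False positives | Sensitivity | Kappa | Bootstrap 95% CI |
|---|---|---|---|---|
| 4/50 | 0 | 92.0% | .953 | .90–.99 |
| 5/70 | 0 | 92.9% | .956 | .91–.99 |
| 6/80 | 0 | 92.5% | .953 | .91–.99 |
| 6/86 | 0 | 93.0% | .956 | .92–.99 |
| 5/80 | 1 | 93.75% | .953 | not run |

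With two or more false positives, kappa does not pass when observed sensitivity is below 94%.

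**Step 2: how often, at the margin?** True positives ~ Bin(P, 0.94) and false positives ~ Bin(450 − P, 1 − specificity), enumerated exactly for every P from 50 to 86.

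| Lollipop specificity | Kappa passes | Formal test passes | Kappa passes, formal fails | Kappa passes, observed sensitivity < 94% |
|---|---|---|---|---|
| 100% | 72–85% | 1–5% | 69–83% | 15–36% |
| 99.75% | 56–70% | 1–5% | 53–69% | 6–21% |
| 99.5% | 39–55% | 1–5% | 36–54% | 2–11% |
| 99% | 15–28% | 1–5% | 13–27% | 0.3–2.5% |
| 98% | 1–5% | 1–5% | 1–4% | at most 0.1% |

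**Step 3: is it an artefact of the assumptions?**
- *Test.* At the same five specificities, a one-sided 0.05 score test gives kappa pass with formal fail in 66–83, 52–67, 36–49, 13–23 and 1–3%. Clopper–Pearson at 0.025 gives 71–83, 56–69, 39–54, 15–27 and 1–4%.
- *Size.* Kappa passes in 70–84% (specificity 100%) and 18–32% (99%) at N=408, and in 73–86% and 12–27% at N=500.
- *Positive count.* At specificity 99%, kappa passes in 6% of trials with 30 positives, 11% with 40 and 24–26% with 100–150.

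**Step 4: both directions for a good swab.** With true sensitivity and specificity both 99%:

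| Positives | 50 | 70 | 80 | 86 |
|---|---|---|---|---|
| Kappa passes, formal fails | 15% | 35% | 12% | 16% |
| Formal passes, kappa at or below 0.95 | 22.5% | 4.4% | 9.7% | 4.1% |

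**Step 5: does the missing alpha matter?** With no misses, the exact lower bound is alpha^(1/P). For 50 of 50 detected it is 0.05^(1/50) = 94.2% (pass) but 0.025^(1/50) = 92.9% (fail). With no misses, a pass needs at least 49 positives at 0.05 and at least 60 at 0.025.

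**The case against.** The strongest reply has four parts.

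1. **Everything is reported anyway.** The estimates, their intervals, the kappa interval and the formal test appear whatever kappa shows, so a reader would see a conflict. Under section 18.1, "the overall care plan will be based on the nasal swab PCR and managed by the school", and lollipop results are not returned to participants. This stands. It limits the harm to the published conclusion and lowers the severity.

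2. **The size depends on a specificity the plan does not give.** A reader might infer that 15–28% is the plan's own scenario because 99% appears in section 20.4. The text does not support that: 99% there is the reference value for PCR, not a projection for the lollipop swab. At 98%, kappa is no more lenient than the formal test. This stands, and is why a range is shown.

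3. **Most conflicts are failures to confirm, not evidence of inferiority.** At specificity 99%, a kappa pass with observed sensitivity below 94% occurs in only 0.3–2.5% of trials. In Step 4 the swab truly is non-inferior, and kappa-only passes mainly reflect the formal test's low power. A reader might also infer that kappa is always the easier rule. It is not: with 50 positives it passes in 53% of trials against 60.5% for the formal test. Nor is a formal pass with kappa at or below 0.95 a contradiction, since the plan makes kappa sufficient, not necessary.

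4. **The rule may be meant for the lower confidence limit.** The text does not say so. That reading would remove the four tables in Step 1 with intervals shown, but not the conflict: 1 miss in 50 with no false positives gives a kappa interval of about .961–1.00, while the exact sensitivity test gives p = 0.19.

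The count of 50–86 positives is also not a bound. Lollipop Only participants (sections 5.1 and 13.1) can enter Aim 2 without an at-school antigen result.

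None of this supplies a ranking or an alpha.

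**Conclusion.** The point holds: section 20.4 is wrong as written and should be fixed. It gives Aim 2 two unranked non-inferiority rules, and the literal kappa rule can override a failed formal test, even with observed sensitivity below the implied 94% bound. For a swab at that bound, kappa passes far more often than the formal test if lollipop specificity is 99.5% or higher, moderately more often at 99%, and no more often at 98%. These sizes rest on the assumed N, positive count, specificity and exact one-sided 0.05 test. The defect in the wording does not.

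A reader might go further and infer that the Aim 2 conclusion is bound to be too favourable, or that participants' care is exposed. The documents support neither: kappa can also be the harder rule, the formal results are reported regardless, and nasal PCR governs care.

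**What to change.** In section 20.4, stop treating kappa as enough on its own. Either report it descriptively with its bootstrap interval, or state that it cannot establish non-inferiority unless the formal test is also met.

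Then state one governing rule: the lollipop swab is non-inferior only if the lower confidence bounds for both sensitivity and specificity against nasal PCR exceed the bound. Give the alpha, the sidedness and the interval method. Confirm that the bound is a fixed 94%. Section 20.4 takes the margin from 99% while also using nasal PCR as the gold standard, and does not explain how the two fit together. The Aim 1 formal test of sensitivity and specificity also has no stated alpha, and the same edit can supply it.

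The cost is text only, with no new procedures, but the rule is stricter and that should be disclosed. At true sensitivity 99%, power for sensitivity is 46–82% with 50–86 positives at one-sided 0.05 (61/49/81/79% with 50/70/80/86), and 0–55% at one-sided 0.025. Specificity is not the constraint: its power is at least 99.9% at true specificity 98.5% or higher.

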## 1.0 Study Summary

Study Title	Safe and Healthy Schools
Brief Summary	This study will target Madison Metropolitan School District school children ages 4-19 and staff who have not had a previous positive COVID-19 test within the past 3 months. It will enroll children and adults for 1-3 days to explore whether serial “at-home” BinaxNOW testing is feasible and non-inferior to “at school” single PCR testing for the evaluation of symptomatic individuals with a negative initial BinaxNOW. It will also explore whether lollipop swabs are more acceptable and perform as well as nasal swabs with PCR testing.
Number of study sites	1
Study Design	Community-based empirical research
Primary Objective	(1) Determine whether “at-home” BinaxNOW testing is feasible for families, (2) Evaluate whether serial “at-home” BinaxNOW testing is non-inferior to “at school” single PCR testing, (3) Compare the acceptability of lollipop swabs and nasal swabs, and (4) Compare the performance of lollipop swabs to nasal swabs with PCR-based testing.
Secondary Objective(s)	NA
Research Intervention(s)/ Investigational Agent(s)	NA
Drugs/devices used on study (including any IND/IDE #)	This study will evaluate the BinaxNOW COVID-19 Ag Card and the “lollipop” swab sample collection method
Study Population	Madison Metropolitan School District school children ages 4-19 and staff
Sample Size	400 with negative at-school BinaxNOW and 50 with positive at-school BinaxNOW. Total n=450.
Study Duration for individual participants	Up to 5 days
Study Specific Abbreviations/ Definitions	PCR: polymerase chain reaction EUA: emergency use authorization

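### Aim 2 lets an observed kappa above 0.95 define the lollipop swab as non-inferior, a rule that can disagree in both directions with the 5-point sensitivity/specificity margin in the same section

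*Combined protocol and SAP*

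**What the plan says.** Section 20.4, Aim 2, gives two routes to a non-inferiority conclusion.

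- **Kappa.** Concordance between nasal and lollipop PCR is measured by kappa with a bootstrap 95% interval. A kappa above 0.95 "will be considered as sufficient to define lollipop swab test non-inferior to the gold-standard PCR testing of nasal swabs". The bar is on the statistic itself, not on its confidence limit.
- **Formal test.** Sensitivity, specificity, PPV and NPV use nasal PCR as reference ("testing as gold standard), and reported along with the corresponding two-sided 95% confidence intervals"). Then: "Formal non-inferiority testing of the lollipop swab test with PCR will be conducted with respect to sensitivity and specificity with a non-inferiority margin of" 5%, with PCR taken as 99% sensitive and specific.

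The section does not say which route decides if they disagree. Section 20.3 defines the Aim 2 population: "we will include all participants who have both nasal and lollipop PCR results". Section 1.0 gives the enrolment: "400 with negative at-school BinaxNOW and 50 with positive at-school BinaxNOW. Total n=450". The plan states no expected positivity, expected kappa or power for Aim 2. The only sample-size calculation, in section 20.2, is for Aim 1.

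**The concern.** Non-inferiority on sensitivity and specificity has a direction and is judged separately among positives and negatives. Kappa pools both kinds of disagreement into one number, depends on the share of positives, and here is used without allowance for sampling error. A fixed cut-off of 0.95 therefore need not agree with a 94% limit on each accuracy measure.

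Aim 2.2 is one of the four primary objectives. Because kappa is called sufficient, a swab whose sensitivity lies at or below the plan's limit could be reported as non-inferior on kappa alone. In the other direction, a swab as accurate as the nasal one could miss the bar and leave the reader with a negative impression.

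**Working it through.** **1. The plan's own figure.** Aim 1 is sized against an NPV of 91%, and section 20.2 gives the target as: "at least 95% with 90% power at the one-sided 0.05 significance level, a sample size of N=358 participants with an initial negative test is required". An exact binomial test reproduces this: rejecting at 335 or more of 358 gives one-sided alpha 0.0487 and power 0.909. The figure concerns Aim 1 only.

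**2. Positivity.** The plan gives none, so it is derived. Section 20.2 says: "The NPV of BinaxNow is ~91% in symptomatic subjects". About 9% of 400 antigen-negatives, or 36, would then be PCR-positive. Adding the 50 antigen-positives, all assumed PCR-positive, gives 86/450 = 19.1%. With the hypothesised 95% instead, it is (20 + 50)/450 = 15.6%.

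**3. Limit.** 99% − 5 points = 94% for both sensitivity and specificity.

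**4. Two possible results with 86 nasal positives of 450.** kappa = (po − pe)/(1 − pe), where po is observed and pe is chance agreement.

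| Lollipop result | Sensitivity | Specificity | po | pe | Kappa |
|---|---|---|---|---|---|
| 6 missed, 0 extra | 80/86 = 93.0% | 364/364 = 100% | 444/450 = 0.9867 | 0.6991 | 0.956, passes |
| 0 missed, 8 extra | 86/86 = 100% | 356/364 = 97.8% | 442/450 = 0.9822 | 0.6798 | 0.944, does not pass |

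Exact binomial tests against 94% give the reverse ranking. For the first result, the probability of 80 or more of 86 at a true 94% is 0.74, so sensitivity is not shown. For the second, sensitivity has p = 0.94^86 = 0.005 and specificity (8 or fewer of 364 at a 6% false-positive rate) has p = 0.0005, so both are shown.

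**5. How often a swab at the limit passes kappa.** Take nasal PCR as the truth, true lollipop sensitivity 94%, 450 pairs and 19.1% positive (multinomial simulation). With specificity 99.95% (assumed), kappa exceeds 0.95 in about 74% of trials. With specificity 99.5% it is about 50%, and with 99% about 27%.

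**6. How often an equally accurate swab passes kappa.** Both swabs are 99%/99% with errors independent given true status. At 19.1%:
- po = 1 − 2 × 0.99 × 0.01 = 0.9802
- share positive on each swab = 0.1911 × 0.99 + 0.8089 × 0.01 = 0.1973
- pe = 0.1973² + 0.8027² = 0.6833
- kappa = (0.9802 − 0.6833)/0.3167 = 0.937

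| Assumption, 450 pairs | Expected kappa at 15.6% / 19.1% | Kappa > 0.95 at 15.6% / 19.1% |
|---|---|---|
| Independent errors | 0.927 / 0.937 | 17% / 28% |
| Nasal PCR error-free, lollipop 99%/99% | 0.963 / 0.968 | 77% / 88% |

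With an error correlation of 0.25 or 0.5 at 19.1%, the pass rate is about 59% or 89%. Under independence, expected kappa exceeds 0.95 only above about 26.7% positivity.

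**7. The formal test under the same assumptions.** The plan gives no significance level for this test, so one-sided 0.025 and 0.05 are shown, using exact tests against 94%. Sensitivity is the limiting part.

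| Assumption | One-sided 0.025, at 15.6% / 19.1% | One-sided 0.05, at 15.6% / 19.1% |
|---|---|---|
| Nasal PCR error-free | 45% / 53% | 55% / 74% |
| Independent errors | 1% / 3% | 2% / 6% |

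In the last row, nasal errors count against the lollipop: its apparent sensitivity at 19.1% is 0.950.

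**The case against.** Four points can be made for the plan.

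- **A reader might infer that a lollipop below the bar would be declared inferior.** The documents do not say so. Kappa above 0.95 is called sufficient, not necessary, and a separate formal test follows. This stands.
- **A reader might infer that the 0.95 cut-off contradicts the assumed 99% accuracy.** The 99% is stated for the formal test, and the plan never assumes independent errors. If nasal PCR is an error-free reference, as the gold-standard wording suggests, an equally accurate lollipop usually passes. This also stands: the rate of missed passes depends on assumptions that the plan does not state.
- **A reader might take lollipop-only positives as extra infections found.** No third test is planned to show that, and against the nasal reference they count as false positives. The second result in step 4 does not need that reading. Even with all 8 counted as false positives, specificity is 97.8% and the formal test succeeds.
- **A swab at the sensitivity limit passes often only if its specificity is very high.** True: the 74% in step 5 falls to 27% at 99% specificity. The single result of 6 misses needs no such model, but it does need nearly all disagreement to be misses.

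These points limit the size of the problem. They do not remove the mismatch between the two rules, or the missing statement of which one decides.

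**Conclusion.** The point holds. A kappa above 0.95 is not a valid stand-in for a 5-point margin around 99%, yet section 20.4 lets it define non-inferiority alone.

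The mismatch needs only the 2×2 table: at 86 nasal positives of 450, the result with 93.0% sensitivity passes kappa, while a result that satisfies the formal test does not. How often this would happen is less certain. A swab at exactly 94% sensitivity passes about 74% of the time with specificity of 99.95%, and less often as specificity falls. An equally accurate swab passes between 17% and 89% of the time, depending on positivity and on how the two swabs' errors are related. All these rates rest on a positivity of 15.6% to 19.1%, derived on the assumption that all 50 antigen-positives are PCR-positive.

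The documents do not support saying that an equivalent lollipop would be declared inferior. They support saying that it could often fail to be shown non-inferior by kappa, and that a swab at or below the limit could be accepted.

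**What to change.** In section 20.4, Aim 2:

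1. Delete the sentence that makes kappa above 0.95 the definition of non-inferiority. Report kappa with its bootstrap interval as description only.
2. State that Aim 2.2 is decided by the formal sensitivity and specificity test already planned, with the 5-point margin, both measures required, and a named one-sided confidence limit compared with 94%.
3. State the expected positivity and the power of that test, including its low success rate if nasal PCR is itself imperfect with independent errors.

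Two substitutes should be avoided. The first is the difference between nasal-only and lollipop-only positives over all participants positive on either swab. It rewards lollipop false positives: at 15% to 20% infected, with independent errors and a one-sided 95% Wald limit against 5 points, a 95%/95% lollipop passes about 95% of the time, against 38% to 52% for an equivalent one. The second is a kappa cut-off set from the observed positivity. It would be fixed after the data are seen, and at the expected value (about 0.92 at 15%) an equivalent swab would still fail about 48% of the time.

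The cost is a change of wording and a power statement, with no new data. The simple single-number rule is lost, and the stated power may look less favourable than the present text suggests.
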